10.4.2. Safety Analyses

Safety analyses will be conducted for the safety population. Adverse events will be coded by the MedDRA dictionary, and TEAEs (ie, AEs reported for the first time or worsening of a pre-existing event after first dose of study treatment) will be tabulated by preferred term and system organ class for all events, related events, and events of Grade 3 or higher. Quantitative safety variables and their changes from baseline (laboratory, vital signs, etc) will be summarized with descriptive statistics. Clinically notable abnormal values will be flagged and tabulated based on predefined criteria. Treatment-emergent AEs of clinical interest (see Section 9.5) will be summarized descriptively by treatment group.

The clinical laboratory data will be analyzed using summary statistics; no formal treatment group comparisons are planned. In addition, distributions of key laboratory parameters may be plotted over time; these values will also be classified into CTCAE toxicity grades and tabulated. Descriptive statistics and mean change from baseline will be determined for vital signs at each assessment time. Vital sign results will be reviewed for clinically notable abnormalities.

[figure not shown]
Descriptive statistics and mean change from baseline will be determined for each ECG parameter at each assessment time. Electrocardiogram results will be reviewed for clinically notable abnormalities according to predefined criteria (see Table 18). Participants exhibiting clinically notable ECG abnormalities will be listed.

Table 18: Criteria for Clinically Notable Electrocardiogram Abnormalities

Parameter	High Threshold	Low Threshold
QTc	> 450 ms	< 295 ms
PR	> 220 ms	< 75 ms
QRS	> 120 ms	< 50 ms
QT	> 500 ms	< 300 ms
RR	> 1330 ms	< 600 ms

Measures of exposure (eg, days of exposure, duration of treatment, average daily dose, and total daily dose) of parsaclisib, placebo, or ruxolitinib will be summarized by means of summary statistics.

10.5. Interim Analysis

There are 2 planned interim analyses for this study. The first interim analysis will be conducted when the first 100 of the planned randomized participants (approximately 50 in each treatment group) reach Week 12 assessments of spleen volume and MFSAF TSS or discontinue treatment. The first interim analysis is to test Week 12 spleen volume and MFSAF TSS for futility. An HSD (Hwang et al 1990) with $\gamma = 0$ will be used to determine the nonbinding futility boundary for spleen volume and MFSAF TSS. The study will be terminated early for futility if either the spleen volume or the MFSAF TSS endpoints cross the futility boundary. Based on the results of this interim analysis, the DMC may recommend to terminate the study, continue the study with no changes to enrollment, or continue the study with no further enrollment permitted until review of the second interim analysis.

The second interim analysis will be conducted when the first 220 randomized participants (approximately 110 in each treatment group) reach Week 12 assessments of spleen volume and MFSAF TSS or discontinue from treatment. The second interim analysis is for the efficacy check at 1-sided alpha of 10%. The study will continue if both spleen volume and MFSAF TSS endpoints are positive. The DMC may recommend to either terminate the study for lack of efficacy or continue the study, based on the results of this analysis.

At both interim analyses, MFSAF TSS will be tested only if spleen volume passes the futility/efficacy check. [Table 19](#) and [Table 20](#) provide the projected stopping rules if the interim analyses are conducted at the projected number of participants.

Table 19: Interim Analysis for Spleen Volume With HSD(0)

	Interim Analysis 1		Interim Analysis 2		Final Analysis	
Number of Participants	100		220		440	
Decision Outcome	Stop for Futility	Continue to Test MFSAF TSS	Stop for Lack of Efficacy	Continue to Test MFSAF TSS	Do Not Reject Null Hypothesis	Reject Null Hypothesis
Z-statistic	≤ 0.18	> 0.18	≤ 1.28	> 1.28	≤ 1.96	> 1.96
One-sided p-value	≥ 0.43	< 0.43	≥ 0.10	< 0.10	≥ 0.025	< 0.025
Parsaclisib plus ruxolitinib response rate ^a	≤ (17.8%, 42.0%)	> (17.8%, 42.0%)	≤ (23.0%, 50.0%)	> (23.0%, 50.0%)	≤ (23.4%, 50.5%)	> (23.4%, 50.5%)

^a Assumes spleen volume response rate for 50 to < 100 × 10⁹/L inclusive and ≥ 100 × 10⁹/L platelet count is 17.2% and 41.0%, respectively, in the ruxolitinib plus placebo group.

Table 20: Interim Analysis for MFSAF TSS With HSD(0)

	Interim Analysis 1		Interim Analysis 2		Final Analysis	
Number of Participants	100		220		440	
Decision Outcome	Stop for Futility	Continue to Interim Analysis 2	Stop for Lack of Efficacy	Continue to the Final Analysis	Do Not Reject Null Hypothesis	Reject Null Hypothesis
Z-statistic	≤ 0.18	> 0.18	≤ 1.28	> 1.28	≤ 1.96	> 1.96
One-sided p-value	≥ 0.43	< 0.43	≥ 0.10	< 0.10	≥ 0.025	< 0.025
Parsaclisib plus ruxolitinib response rate ^a	≤ (35.4%, 46.9%)	> (35.4%, 46.9%)	≤ (42.8%, 54.6%)	> (42.8%, 54.6%)	≤ (43.6%, 55.5%)	> (43.6%, 55.5%)

^a Assumes TSS response rate for 50 to < 100 × 10⁹/L inclusive and ≥ 100 × 10⁹/L platelet count is 34.5% and 45.9%, respectively, in the ruxolitinib plus placebo group.

Preplanned analyses of safety and efficacy will be provided to an independent DMC as specified in the DMC charter. The process by which the DMC will review data and make recommendations and decisions will be documented in the DMC charter.

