2.6.1.4. Potential Benefits of Piasaalisib

The ongoing Phase 2 study showed that additional alleviation of both symptoms and splenomegaly occurred when the PI3K δ inhibitor piasaalisib (INCB050465) was added to

participants on a stable ruxolitinib regimen. Specifically, at the time of efficacy data cutoff of 27 AUG 2020, 35 participants had been enrolled to receive all daily dosing regimens (18 dosed with 5 mg QD from Day 1 forward and 17 dosed with 20 mg QD for the first 8 weeks followed by 5 mg QD going forward). The median reduction in spleen volume at 12 and 24 weeks was 13.0% and 21.8%, respectively. Seven of 23 participants (30%) had at least 25% reduction in spleen volume at Week 24. Thirty percent of participants had 50% reduction in TSS at Week 12 and 19% at Week 24 (Yacoub et al 2021). These preliminary findings in the difficult-to-treat ruxolitinib-refractory population suggest that the combination of piasalisib and ruxolitinib may also be efficacious in JAK- and PI3K-naïve patients with MF.

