- Absolute neutrophil count has been $> 1.0 \times 10^9/L$ since the last scheduled study visit.

Doses may not exceed 10 mg BID except in participants who continue to meet the above dose-escalation criteria [REDACTED]

[REDACTED] while receiving 10 mg BID. Such participants may continue dose escalation to a maximum dose of 15 mg BID. Note that when a 5 mg QD increment is added, creating a regimen such as 5 mg/10 mg, the higher dose should be taken in the evening and the lower dose in the morning.

Doses may never exceed 15 mg BID.

No dose increases after Week 16 are allowed except for dose increases related to a recovery from a prior dose reduction or hold.

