10. STATISTICS

10.1. Sample Size Determination

The primary endpoint of this study is the proportion of participants with $\geq 35\%$ spleen volume reduction from baseline to Week 24 as measured by MRI (or CT scan in applicable participants). The primary endpoint will be analyzed by CMH test stratified by DIPSS (intermediate-1 vs intermediate-2 vs high) and baseline (or screening, if applicable) platelet count ($\geq 100 \times 10^9/L$ vs 50 to $< 100 \times 10^9/L$ inclusive; note that if a participant's platelet count is $< 50 \times 10^9/L$ at baseline, the platelet count at screening will be used for stratification/randomization). Assuming a 58.2% (29.4%) response rate for participants with normal (low) platelet count for the ruxolitinib plus piasalisib group versus 41.0% (17.2%) response rate for participants with normal (low) platelet count for the ruxolitinib plus placebo group, to achieve 83.67% power to detect a statistically significant difference with a 2-sided Type I error of 5%, a sample size of 440 participants is required to be randomized equally between treatment groups.

For the key secondary endpoint of proportion of participants who have a $\geq 50\%$ in MFSAF TSS from baseline to Week 24, assuming a response rate of 61.7% (50.0%) for participants with normal (low) platelet count for the ruxolitinib plus piasalisib group and a response rate of 45.9% (34.5%) for participants with normal (low) platelet count for the ruxolitinib plus placebo group, a sample size of 440 will provide 80.02% power using CMH test given a 2-sided Type I error of 5%.

A test for OS will be performed when 85 deaths are observed using the log-rank test stratified by platelet count and DIPSS at baseline at a 2-sided Type I error level of 0.05. The log-rank test will provide 80% power to detect a hazard ratio of 0.54. Assuming a median survival time of 5.3 years for ruxolitinib plus placebo and enrollment duration is 1.5 years, the expected time to analysis from the first participant randomized is 3 years.

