10.2. Derivations and Calculations for Interim Analyses

For the first analysis of futility, the gamma spending function with spending parameter equal to 0 will be used to allocate beta-spending based on a Type II error of 0.16 for spleen volume reduction and 0.2 for MFSAF TSS under the alternative hypothesis. [Figure 1](#) shows that the beta spending function allocates minimal beta for the first interim analysis.

As no formal decision for efficacy will be made based on the efficacy check in the second interim analysis, no alpha will be spent.

Figure 1: Beta Spending

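### The Interim 1 futility boundary, the interim response-rate projections and the stated power treat Week 12 response as Week 24 response, with no Week 12 assumption or justification

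*Protocol*

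**What the plan says.** **Planning rates (Protocol 10.1, SAP 3.3).** "The primary endpoint of this study is the proportion of participants with $\geq 35\%$ spleen volume reduction from baseline to Week 24". The rates are for that endpoint: "Assuming a 58.2% (29.4%) response rate for participants with normal (low) platelet count" on parsaclisib, "versus 41.0% (17.2%) response rate for participants with normal (low) platelet count for the ruxolitinib plus placebo group". For Week 24 TSS response they are 61.7% (50.0%) and 45.9% (34.5%). With 440 participants the stated powers are 83.67% and 80.02%.

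**Interims (Protocol 10.5, SAP 10.1).** "The first interim analysis is to test Week 12 spleen volume and MFSAF TSS for futility". Both looks, at 100 and 220 participants, test Week 12 spleen and TSS response. Interim 1 uses an HSD boundary with gamma 0 and stops at Z ≤ 0.18. Interim 2 is a 1-sided 10% test and stops at Z ≤ 1.28.

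**Basis of the boundary and tables.** SAP 10.2 allocates beta "based on a Type II error of 0.16 for spleen volume reduction and 0.2 for MFSAF TSS under the alternative hypothesis". The only alternative in either document is the Week 24 one. The footnotes to Protocol Tables 19-20 and SAP Tables 6-7 apply one set of control rates (spleen 17.2%/41.0%, TSS 34.5%/45.9%) to the interim and final columns alike.

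**Status of the rules.** Protocol 10.5 says the study ends if either endpoint crosses at Interim 1, and that it goes on after Interim 2 if both are positive. The same section calls the Interim 1 boundary nonbinding and leaves the DMC to recommend. SAP 3.2 calls the rules at both interims nonbinding.

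**Phase 2 (Protocol 2.6.1.4).** "The median reduction in spleen volume at 12 and 24 weeks was 13.0% and 21.8%, respectively". The share of participants with a 50% TSS reduction was 30% at Week 12 and 19% at Week 24.

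**The concern.** The trial's question is benefit at Week 24. A futility look on an earlier measure protects that question only if the expected early effect has been thought through. Here it is silently set equal to the Week 24 effect, and the headline power depends on that. If the spleen difference is still building at Week 12, a drug with the full planned Week 24 benefit has a materially higher chance of meeting a stop rule than the sponsor or the DMC has been told. The DMC would also have no documented Week 12 expectation against which to judge a failed check.

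**Working it through.** **Inputs.** Rates, sample sizes and boundaries are as above. The low-platelet share is not stated; 20% is assumed, with 10-30% as the range. DIPSS strata and dropout are ignored.

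**Formula.** With stratum weights w, rate difference d = Σw(p_T − p_C), variance V = Σw·2p̄(1−p̄) and n per arm, the CMH statistic has mean μ = d√n/√V.

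**Spleen, Week 24 rates.**
- d = 0.8 × 0.172 + 0.2 × 0.122 = 0.162
- V = 0.8 × 2(0.496)(0.504) + 0.2 × 2(0.233)(0.767) = 0.4715
- μ = 1.668 (n = 50), 2.475 (n = 110), 3.499 (n = 220)

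**Reproducing the stated power.**
- Single look at 440: Φ(3.499 − 1.96) = 94%. Across the platelet range this is 93-95% for spleen and 91-92% for TSS. It does not match the plan.
- Passing Z > 0.18, Z > 1.28 and Z > 1.96 in turn, with all three looks at Week 24 rates and correlation √(n_i/n_j): spleen 83% (82-85% across platelet shares and variance forms), TSS 79.2-80.3%. Spleen equals exactly 83.67% at a low-platelet share of 14% (pooled variance) or 23% (unpooled).

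The stated powers therefore already include both Week 12 gates, at full Week 24 rates.

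**Reproducing the boundary.** Linear (HSD gamma 0) spending in a two-look design at 100 and 220, 1-sided 10%:
- Spleen: beta at the first look = 0.16 × 100/220 = 0.0727, z = −1.456. A design with total Type II error 0.16 has μ = 1.627 at the first look, so the boundary is 1.627 − 1.456 = 0.17.
- TSS: beta = 0.20 × 100/220 = 0.0909, z = −1.335, giving 1.520 − 1.335 = 0.185.

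Both agree with the printed 0.18. Spending at fraction 100/440 gives about −0.39 to −0.36 and does not fit.

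**Letting Week 12 differ.** The Week 12 spleen difference is a fraction of the Week 24 difference, the Week 24 effect is as planned, and the rules are followed:

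| Week 12 / Week 24 difference | Fails Interim 1 | Fails Interim 2 | Meets either stop rule | Power |
|---|---|---|---|---|
| 100% | 7% | 12% | 15% | 83% |
| 90% | 9% | 17% | 21% | 78% |
| 80% | 12% | 24% | 28% | 71% |
| 60% | 20% | 41% | 45% | 54% |

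The Interim 2 column is the chance at that look taken alone.

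**Sensitivity.**
- Low-platelet share 10-30%: 14-16% meet either rule at 100%, 27-29% at 80%, 44-46% at 60%.
- A Week 12/Week 24 correlation of 0.7 instead of 1 lowers power by about one point.
- A 200,000-run binomial simulation gave 14% at 100% and 45% at a ratio of 0.596.
- Scaling both arms' Week 12 rates by 0.596, instead of the difference, gives 39% and power of 59-60%.
- Adding the TSS gate at its full planned effect (endpoint correlation 0.5 to 0) gives 25-29% as designed, and 50-55% with spleen at 0.596.

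**Effect on the Interim 1 boundary.** For the same spleen beta, the boundary is μ − 1.456:
- 100%: 1.668 − 1.456 = 0.21
- 80%: 1.339 − 1.456 = −0.12
- 60%: 1.009 − 1.456 = −0.45

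With no effect at all, the chance of stopping at that look is Φ(0.18) = 57%, Φ(−0.12) = 45% and Φ(−0.45) = 33%.

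**The case against.** **The Phase 2 ratio is not an estimate.** 13.0/21.8 = 0.60, so a reader might infer that 60% of the effect is present at Week 12 and that an effective drug would often be stopped. The documents do not support this. The figures are medians of within-patient change, without a control, in an add-on study of participants with suboptimal response to ruxolitinib. There were 35 participants on two dosing regimens; 23 enter a Week 24 count, and the Week 12 number is not given. They say nothing direct about a between-arm difference in 35% response in JAK-naive participants. This objection stands. It limits what the 60% row can mean, but the undeclared equality remains.

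**TSS points the other way.** Response was higher at Week 12 than at Week 24, so there is no support for a Week 12 shortfall on that endpoint. This stands.

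**The rules are nonbinding.** Meeting a stop rule is not the same as stopping. The DMC decides under a charter that is not among the documents, and at Interim 1 it may also pause enrolment until Interim 2. This stands, so the power figures apply only if the rules are followed.

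**Interim 2 is not built on Week 24 rates.** Z > 1.28 is a plain 10% test, valid at any rates. Only its projected response rates and its false-stop risk depend on them. This stands.

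**Titration.** For the low-platelet stratum, Protocol 6.7.1.3 says: "No dose increases after Week 16 are allowed except for dose increases related to a recovery from a prior dose reduction or hold". One might infer that Week 12 understates the treatment difference. But increases are optional, the rule is the same in both blinded arms, and in the other stratum they end at Week 8. Unsettled background dosing in both arms does not show a smaller difference.

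**An early-endpoint futility look is a recognised choice.** Agreed. The point concerns its undeclared assumption, not its use.

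**Conclusion.** The point holds as a defect in the planning assumptions. The Interim 1 boundary, the interim response-rate cells and both stated powers equate Week 12 with Week 24, and the reproduction of 83.67% and 80.02% confirms it. The Phase 2 figures give reason to doubt the equality without saying how far it fails.

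The size depends on a ratio that nobody has stated. A 20% shortfall in the Week 12 spleen difference costs about 12 points of power (83% to 71%); a 40% shortfall costs about 29 (83% to 54%). These figures assume the rules are followed, spleen alone, 20% low platelets and the full planned Week 24 effect. They do not show that the drug would be slow, or that the trial would be stopped.

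**What to change.** 1. In Protocol 10.5 and SAP 10.2/10.3, state assumed Week 12 control and treatment rates for each endpoint, with their basis. Re-derive the Interim 1 boundary and the response-rate cells at both interims from them.
2. In Protocol 10.1 and SAP 3.3, say that the stated power includes the Week 12 stops, and report power for Week 12 effects of 60-100% of Week 24.
3. In Protocol 10.5 and SAP 10.1, reconcile the wording that the study ends with the nonbinding status in the same sections and in SAP 3.2.

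**Cost.** A protocol and SAP amendment and some computation; no added participants or visits. The stated power becomes less favourable, and a lower Interim 1 boundary stops an ineffective drug less often at that look. The new boundary alone recovers little power: at 60%, failing Interim 2 accounts for 41 of the 45 points. This is why the power range should be shown.

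**Optional.** The sponsor could consider a predictive probability at Interim 2 that uses Week 24 results already in hand. With even accrual (440/18 = 24.4 a month), the 220th participant enters at month 9.0 and reaches Week 12 at about month 11.8. Those enrolled by month 6.2, about 152, would then have passed Week 24. Slower early accrual would lower this; a linear ramp gives about 135, before image-reading time. This option needs a model linking Week 12 to Week 24 and a threshold, and it is a trade-off, not a required change.

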3.2. Control of Type I Error

This study defines a single primary endpoint with a single primary analysis. The study will be claimed to have achieved the primary efficacy objective when the primary endpoint shows a significant result at 2-sided alpha of 0.05 at final analysis. The secondary efficacy endpoints will be analyzed only when the study has reached the efficacy objective in the primary endpoint. The key secondary efficacy variables will be tested following a fixed-sequence-testing procedure with each at the 2-sided alpha level of 0.05 in the order below:

1. The proportion of participants who have a $\geq 50\%$ reduction from baseline to Week 24 in MFSAF TSS
2. Overall survival

Other secondary [REDACTED] endpoints will be tested using a 2-sided, 5% significance level; however, these are not considered alpha-controlled hypotheses.

There are 2 planned interim analyses in this study, both aiming to terminate the study if there is inadequate efficacy. The nonbinding futility rules in Interim Analyses 1 and 2 will control the probability of continuing beyond Interim Analysis 2 at 10%. As no formal decision for efficacy will be made based on these interim analyses, no overall alpha will be spent.

An independent DMC will be assembled to monitor safety data, efficacy data, and study conduct on a regular and ongoing basis during the study. See Section 10 for details regarding the alpha-spending plan and interim analyses conducted in this study.

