3.3. Sample Size Considerations

The primary endpoint of this study is the proportion of participants with $\geq 35\%$ spleen volume reduction from baseline to Week 24 as measured by MRI (or CT scan in applicable participants). The primary endpoint will be analyzed by CMH test stratified by DIPSS category (intermediate-1 vs intermediate-2 vs high) and baseline platelet count ($\geq 100 \times 10^9/L$ vs 50 to $< 100 \times 10^9/L$ inclusive). Assuming a 58.2% (29.4%) response rate for participants with normal (low) platelet count for the ruxolitinib plus parsaclisib group versus 41.0% (17.2%) response rate for participants with normal (low) platelet count for the ruxolitinib plus placebo group, to achieve 83.67% power to detect a statistically significant difference with a 2-sided Type I error of 5%, a sample size of 440 participants is required to be randomized equally between treatment groups.

For the key secondary endpoint of proportion of participants who have a $\geq 50\%$ in MFSAF TSS from baseline to Week 24, assuming a response rate of 61.7% (50.0%) for participants with

normal (low) platelet count for the ruxolitinib plus parsaclisib group and a response rate of 45.9% (34.5%) for participants with normal (low) platelet count for the ruxolitinib plus placebo group, a sample size of 440 will provide 80.02% power using CMH test given a 2-sided Type I error of 5%.

A test for OS will be performed when 85 deaths are observed using the log-rank test stratified by platelet count and DIPSS category at baseline at a 2-sided Type I error level of 0.05. The log-rank test will provide 80% power to detect a hazard ratio of 0.54. Assuming a median survival time of 5.3 years for ruxolitinib plus placebo and enrollment duration is 1.5 years, the expected time to analysis from the first participant randomized is 3 years.

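### The stated power (83.67% spleen, 80.02% TSS) does not reflect the two-endpoint stopping rules as written; if those rules are followed, primary power is about 67-74%.

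*Protocol*

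**What the plan says.** Protocol 10.1 sizes the trial on the Week 24 spleen response, with 440 participants "to achieve 83.67% power to detect a statistically significant difference with a 2-sided Type I error of 5" percent. For the TSS response, "a sample size of 440 will provide 80.02% power using CMH test given a 2-sided Type I error of 5" percent. SAP 3.3 repeats both figures. Neither section mentions the interim analyses.

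Protocol 10.5 and SAP 10.1 set two looks at Week 12 data, after 100 and 220 participants. At the first, "The study will be terminated early for futility if either the spleen volume or the MFSAF TSS endpoints cross the futility boundary". At the second, "The study will continue if both spleen volume and MFSAF TSS endpoints are positive". Protocol Tables 19 and 20 (SAP Tables 6 and 7) give both endpoints the same Z boundaries: 0.18, 1.28 and a final 1.96. Table 20 labels a TSS Z of 1.28 or less at the second look as a stop for lack of efficacy.

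The rules are advisory. SAP 3.2 calls them nonbinding at both looks, and Protocol 10.5 says of the second: "The DMC may recommend to either terminate the study for lack of efficacy or continue the study, based on the results of this analysis".

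SAP 10.2 treats the endpoints separately, using the spending function to "allocate beta-spending based on a Type II error of 0.16 for spleen volume reduction and 0.2 for MFSAF TSS under the alternative hypothesis". SAP 3.2 adds: "The nonbinding futility rules in Interim Analyses 1 and 2 will control the probability of continuing beyond Interim Analysis 2 at 10" percent.

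**The concern.** Under the written rules, a weak Week 12 result on TSS, a secondary endpoint, can end the trial before the primary endpoint is tested. Primary power under those rules must therefore be lower than power with the spleen boundaries alone, and lower again than power with no stopping. The plan gives one power per endpoint and does not say which of these situations it describes.

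At stake is the chance of abandoning a drug that works as assumed. The DMC is asked to consider ending a 440-participant Phase 3 trial, and neither document gives the risk that following the rules stops it wrongly.

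**Working it through.** **Inputs from the documents.** Response rates, normal (low) platelets: spleen 58.2% (29.4%) against 41.0% (17.2%); TSS 61.7% (50.0%) against 45.9% (34.5%). There are 220 participants per arm. Looks are at 100, 220 and 440 participants, with boundaries 0.18, 1.28 and 1.96.

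**Assumptions not in the documents.** Low-platelet share 10-30%; correlation r between the two Z statistics at the same look 0-0.5; Week 12 effect equal to Week 24 effect (Tables 19 and 20 use the same control rates at all looks); pooled or unpooled variance.

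**Step 1: drift of the stratified CMH statistic.** With n_h per arm in stratum h, drift = Σ(n_h/2)(p1 − p0) / √Σ(n_h/2)·p̄(1 − p̄). At a 15% low share, n_h is 187 and 33:

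- Spleen: (93.5×0.172 + 16.5×0.122) / √(93.5×0.496×0.504 + 16.5×0.233×0.767) = 18.095/√26.322 = 3.527.
- TSS: (93.5×0.158 + 16.5×0.155) / √(93.5×0.538×0.462 + 16.5×0.4225×0.5775) = 17.33/√27.27 = 3.319.

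**Step 2: no stopping.** Φ(3.527 − 1.96) = 94.1% for spleen and Φ(3.319 − 1.96) = 91.3% for TSS. The stated figures do not reproduce. At a 15% share, about 170 per arm would be enough for either stated power, even with a continuity correction.

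**Step 3: each endpoint against its own boundaries.** P(Z1 > 0.18, Z2 > 1.28, Z3 > 1.96), with means drift×√(n_i/440) and correlations √(n_i/n_j), gives 83.6% for spleen and 79.3% for TSS (unpooled: 84.6% and 80.3%). These are close to 83.67% and 80.02%. The separate Type II errors in SAP 10.2 point the same way: 1 − 0.8367 = 0.163 and 1 − 0.8002 = 0.200.

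**Step 4: joint rule as written.** Both endpoints must exceed 0.18 at the first look and 1.28 at the second, and spleen must then exceed 1.96. The correlation between endpoints across looks is r×√(n_i/n_j). Results in percent, from 2 million simulated paths per setting:

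| Quantity | 15% share, pooled; r = 0 / 0.3 / 0.5 | Range over all settings |
|---|---|---|
| Primary, no stopping | 94.1 | 93-95 |
| TSS, no stopping | 91.3 | 91-92 |
| Primary, own boundaries only | 83.6 | 82-85 |
| TSS, own boundaries only | 79.3 | 79-80 |
| **Primary, joint rule at both looks** | **68.9 / 70.9 / 72.6** | **67-74** |
| Primary, then TSS, joint rule | 66.3 / 68.5 / 70.4 | 65-72 |
| Primary, joint rule at first look only | 81.9 / 82.8 / 83.6 | 81-85 |
| Primary, joint rule at second look only | 74.1 / 75.7 / 77.1 | 73-79 |
| False stop at first look | 14.2 / 13.4 / 12.6 | 12-15 |
| Further false stop at second look | 15.2 / 14.0 / 13.2 | 12-16 |
| Total false stop | 29.3 / 27.4 / 25.8 | 24.4-30.5 |

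With the spleen boundaries only, the total false-stop risk is about 14-16% (pooled variance). Most of the power loss comes from the second look.

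**Step 5: checks.** A participant-level simulation applying the CMH test, at a 15-20% low share, gave 69-72% for the primary endpoint under the joint rule. With r = 0.8, primary power is about 75-77%; even at r = 0.99 it is about 80-81%. At a 15% share, a within-person Week 12/Week 24 correlation of 0.5-0.9 gives 67-72%. A Week 12 effect at 90% of the Week 24 effect gives 60-65%; at 110% it gives 77-79%.

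**Step 6: no effect.** One endpoint passes both looks 9.0% of the time. Both endpoints do so 0.8%, 1.8% or 2.8% of the time (r = 0, 0.3, 0.5). The 10% in SAP 3.2 therefore also looks like a one-endpoint figure.

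**The case against.** The strongest reply is that no stated figure is shown to be miscalculated. The two powers can be read as describing each endpoint's own test, and the rules are nonbinding, so 67-74% is a full-adherence figure and not expected power. That last part stands. If the DMC overrides every stop, power is about 93-95%. But the stated 83.67% is not the no-stopping figure either: it appears to allow for stopping on one endpoint while the written rules use two.

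The numerical match does not prove how power was calculated. A fixed design with 70% of the information and no stopping would give 83.9% and 79.3%. The 0.18 boundary also does not follow from the spending described: linear spending of 0.16 uses 0.16×100/440 = 0.036 at the first look, whereas P(Z1 ≤ 0.18) under the assumed drift is about 0.067. The first-look response rates in Tables 19 and 20 imply a Z of about 0.10. Using 0.10 raises joint power by only about 1 point. These points stand as limits on the inference about method; they do not close the gap.

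SAP 3.2 is not wrong if its 10% is read as an upper limit, since 0.8-2.8% is below it. The conclusion does not need that remark. The DMC charter, which was not available, may contain joint false-stop probabilities, but it could not correct the power stated in Protocol 10.1 and SAP 3.3.

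**Conclusion.** The concern holds. With the joint rules followed at both looks, primary power is about 10 to 17 points below the stated 83.67%, and the risk of stopping an effective drug is nearly double the risk under the spleen boundaries alone. The stated figure matches neither full adherence to the written rules nor full override of them.

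The exact size rests on the undocumented inputs listed in the working, and the Week 12 effect matters most: varying it by 10% either way moves primary power between about 60% and 79%. No between-endpoint correlation or platelet share tried brings the joint figure up to 83.67%. That the sponsor calculated power one endpoint at a time is an inference. Type I error and the final analysis are unaffected.

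**What to change.** In Protocol 10.1 and SAP 3.3 and 10:

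- State which stopping rules the 83.67% and 80.02% assume.
- Report power under the joint rules as a range, naming the assumed between-endpoint correlation, low-platelet share and Week 12 effect. Place it beside the no-stopping figures.
- Say in SAP 3.2 whether the 10% refers to one endpoint or both.
- Give the DMC the matching false-stop probability at each look.

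The cost is wording and a short simulation, and the published power becomes less favourable. The correction itself needs no design change and no extra participants. Whether to alter the interim rules or the sample size afterwards is a separate decision for the sponsor.
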